Statistical analysis plan for Safer Births Bundle of Care, phase II

Version: 1.0 Date: October 28, 2025

This Statistical Analysis Plan (SAP) describes analytical approaches for the assessment of intervention effects on perinatal and maternal (clinical) outcomes of the Safer Births Bundle of Care (SBBC) project, phase II (registered as ISRCTN92381311), and for exploring promotors and inhibitors for change. It was finalized before completion of the data, but after some preliminary, descriptive analyses on partial data, including observed rates of outcome over time and assessment of missingness.

1 Introduction

SBBC phase II is a quality improvement study, implemented in 142 facilities in five regions in Tanzania. These facilities comprise all CEmONC (Comprehensive Emergency Obstetrics and Newborn Care) facilities in these five regions. Among the facilities, 30 took part in SBBC phase I and 112 facilities are new. As such, SBBC phase II represents an upscaling but also introduced new elements vis a vis SBBC phase I, see the protocol at https://www.isrctn.com/ISRCTN92381311 for details.

Identification of eligible facilities and central preparations started in December 2023. From January 2024 preparations for the implementation took place at the individual facilities, and the intervention started April-June 2024.

2 Data

Baseline data from 2023 and the first months of 2024 were collected retrospectively from prospectively registered births in hospital books for the 112 new facilities. For the 30 facilities continuing from SBBC phase I, baseline data from this period were gathered prospectively via the data system set up for SBBC phase I. From March 2024, designated data collectors visited all facilities regularly i.e. at least biweekly, registering data on newly recorded births from hospital books.

Recorded information from hospital books included outcomes and clinical variables (mother's age and parity, child's gender, birth weight, number of fetuses, etc.) related to the child and the mother. Every child and every birth have a unique ID number. Unfortunately, repeated births by the same mother cannot be identified.

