2.1 Outcomes

Two primary outcomes were listed in the protocol, and are defined as:

- Perinatal death defined as intrapartum stillbirth (ISB) or newborn death within the first 24 hours of life.
- Maternal death within seven days postpartum.

Unfortunately, death within 24 hours is not directly available in the collected data from hospital books, apart from for newborns admitted to NICU. For all others, we have status at discharge and date (but not time of day) of discharge. We will define "early newborn death" as discharged as dead within (i.e., including) the date of birth plus one day. Which means that, depending on the time of day of the birth, death may have occurred at most <48 hours after birth.

Similarly, seven days maternal mortality will be defined as being dead at discharge if date of discharge for the mother is at most seven days after the date of delivery. (If date of discharge is missing for mother, we will impute it using date of discharge for child.)

For the baseline data from SBBC-I facilities, we do have the 24-hour newborn deaths and the sevendays maternal deaths directly available. However, to make the rates comparable, we will apply the same definitions to these data as well.

For perinatal death, newborns that are referred out during the first 24 hours will be regarded as having unknown outcome. Antepartum/macerated stillbirths (ASB) will be excluded from the sample. For maternal death, mothers referred out before seven days will be considered to have unknown outcome. ASB will be included and used as an adjustment variable when considering maternal outcome.

The following secondary outcomes were defined:

- 24-hour newborn death.
- Intrapartum stillbirth (ISB).
- 7-days perinatal death (including ISB).

The 24-hour newborn deaths will be redefined as "early newborn deaths" as above. Seven-days newborn deaths will be assessed using status at discharge and date of discharge as for maternal outcome.

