3.2 Estimation of overall efficacy

Logistic regression will be used to assess the overall efficacy of the intervention, including data from all 142 facilities. We anticipate varying intervention effects per region and per facility level and depending on whether the facility was part of SBBC phase I or not, and possibly also varying intervention effects between combinations of these factors. Further, we anticipate time-varying intervention effects as well as clustering on two levels, birth (for multiples) and facility.

Thus, the full model will be a mixed-effects logistic regression model, incorporating the following:

Fixed effects:

- a) Time-varying intervention effects modelled using a continuous variable representing time since intervention start (set to zero for all baseline observations). To capture potential nonlinear effects, time will be modelled using splines. The spline-transformed time variable, f(t), will be interacted with an indicator for intervention status (intervention vs. baseline), i.e., I(intervention).
- b) Region-specific treatment effects, modeled through an interaction between region (five regions) and the intervention-by-time spline term, $I(\text{intervention}) \cdot f(t)$.
- c) Facility level-specific treatment effects, modeled through an interaction between facility level (three levels) and $I(\text{intervention}) \cdot f(t)$.
- d) Differing treatment effects between facilities that were part of SBBC phase I and those new in SBBC phase II, through interaction between SBBC-I (yes/no) and I(intervention) $\cdot f(t)$.
- e) All higher level interactions between region, facility level, SBBC-I, and $I(\text{intervention}) \cdot f(t)$.

Random effects:

f) Random effects (random intercepts and random intervention effects) for facilities and for births nested within facilities.

In Stata syntax, the full regression model looks like this:

```
i.region i.facility_level i.sbbc_phase1 i.intervention ///
i.intervention#c.s_time ///
i.region#i.intervention#c.s_time ///
i.facility_level#i.intervention#c.s_time ///
i.sbbc_phase1#i.intervention#c.s_time ///
i.region#i.facility_level#i.intervention#c.s_time ///
```

```
i.region#i.sbbc_phase1#i.intervention#c.s_time ///
i.facility_level#i.sbbc_phase1#i.intervention#c.s_time ///
i.region#i.facility_level#i.sbbc_phase1#i.intervention#c.s_time ///
|| facility_id: i.intervention i.intervention#c.s_time ///
|| birth_id: i.intervention i.intervention#c.s_time ///
, covariance(unstructured)
```

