For the new SBBC-II sites, we have two sources of baseline data, each with its own limitations and merits. The retrospective data from 2023 and two first months of 2024 are not affected by the intervention in any way and represent a large sample. On the other hand, the data quality is expected to be lower than for the prospective data and with under-reporting of mortality. The prospective baseline data were collected in a period with preparation for the intervention, training of champions, probably increased awareness of optimal birth care, and possibly a Hawthorne effect related to the awareness of being observed/"measured". The data quality is more similar to that of the data collected during the intervention period, but the sample size is smaller than for the retrospective baseline data.

The relative effects of the expected more complete reporting of poor outcomes and the impact of the preparations in the prospective baseline data are unknown, but we believe that the underreporting in the retrospective data is substantial. We will present some analyses comparing the prospective and the retrospective baseline data, to inform the discussion of results of the main analyses.

8 Software

The analyses will be performed in Stata version 18 and R version 4.5.1, or newer versions.

9 References

ISRCTN92381311. Scaling up safer births bundle of care - keeping more mothers and babies safe during and after birth. ISRCTN Registry; 2025. Available at: https://www.isrctn.com/ISRCTN92381311.

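### The supplementary comparison of intervention effects between SBBC-I and new facilities can differ from 1 through recording alone, because the two groups' baseline data come from different sources

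*SAP*

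**What the plan says.** **Data sources (section 2).** Baseline data were "collected retrospectively from prospectively registered births in hospital books for the 112 new facilities". For the 30 continuing facilities, "baseline data from this period were gathered prospectively via the data system set up for SBBC phase I". After that there is one method for everyone: "From March 2024, designated data collectors visited all facilities regularly i.e. at least biweekly, registering data on newly recorded births from hospital books".

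**Outcomes (section 2.1).** For the SBBC-I baseline, "we do have the 24-hour newborn deaths and the sevendays maternal deaths directly available". The book data give status and date at discharge, with 24-hour death directly available only for newborns admitted to NICU. The SAP applies the discharge-based definitions to the SBBC-I baseline as well, so that rates are comparable.

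**Use of the contrast.** Section 3.2 item d provides for "Differing treatment effects between facilities that were part of SBBC phase I and those new in SBBC phase II", through an interaction of SBBC-I status with the intervention-by-time spline. Section 7 presents marginal RRs by combinations of region, facility level and SBBC-I status. Section 3.3 plans separate CUSUM charts by SBBC-I status, and section 5 uses the same baseline models for the VLAD plots.

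**Acknowledged limits.** Section 7 says "For the new SBBC-II sites, we have two sources of baseline data, each with its own limitations and merits". It regards under-reporting in the retrospective part as substantial, and plans a comparison of the retrospective and prospective baselines to inform discussion. Section 4 rules out causal claims and treats every p-value outside the two co-primary efficacy estimates as exploratory.

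**The concern.** A before-after RR within a group is the true effect multiplied by the change in the share of deaths recorded. If that change is the same in both groups, it cancels when their RRs are compared. Here there is no reason to expect it to be the same: new facilities go from retrospective to regular extraction from the same kind of books, while SBBC-I facilities go from a prospective study system to book extraction.

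Nothing planned removes or tests this:

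- Section 2.1 aligns the outcome definition, not the completeness with which deaths are captured.
- The SBBC-I main effect in the section 3.2 model absorbs a constant difference in level, not a group-specific change at the switch of source.
- The best-case and worst-case scenarios in section 6 concern missing outcomes of recorded births, not deaths left unrecorded or a change of source.
- The section 7 comparison of baseline sources is confined to the new sites.
- Section 3.2 discusses the SBBC-I comparison only in terms of case mix and referral patterns.

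At stake is the message a reader takes from two RRs printed side by side. Facilities with phase I experience could appear to gain more than newcomers, or the reverse, when the effect is the same in both. A group's CUSUM or VLAD would carry the same distortion, because its expected deaths come from that group's baseline recording.

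**Working it through.** The SAP states no figure for this contrast, so there is nothing to reproduce. The check asks how large a spurious ratio of RRs could be when the true effect is identical in both groups.

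**Inputs from the SAP**
- Retrospective baseline at new sites: 14 months ("The retrospective data from 2023 and two first months of 2024 are not affected by the intervention"; 12 + 2 = 14).
- Prospective baseline: from March 2024 until "the intervention started April-June 2024", taken as m = 1 to 3 months. The baseline is then 15 to 17 months, and the retrospective share is 14/17 = 82% to 14/15 = 93%.
- Direction at new sites: lower capture in the retrospective data (section 7).

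**Assumptions, because the SAP gives no figures**
- c: capture of deaths in the retrospective months relative to later book extraction, 0.7 to 0.9.
- s: capture in the SBBC-I system before March 2024 relative to later book extraction. The main case is s = 1. That the SBBC-I sites switched in March 2024 is inferred from section 2, which says all facilities were visited from then. The date does not matter when s = 1.
- Births per month constant; no effect of the preparation period.

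**Formulas**
- New sites: observed RR = true RR × (14 + m)/(14c + m).
- SBBC-I sites: observed RR = true RR × (14 + m)/(14s + m).
- Ratio new/SBBC-I = (14s + m)/(14c + m). A common true RR cancels.

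**Main case, s = 1**

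| c | m = 1 | m = 3 |
|---|---|---|
| 0.9 | 15/13.6 = 1.10 | 17/15.6 = 1.09 |
| 0.8 | 15/12.2 = 1.23 | 17/14.2 = 1.20 |
| 0.7 | 15/10.8 = 1.39 | 17/12.8 = 1.33 |

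For illustration, take a common true RR of 0.80. The SBBC-I stratum shows 0.80, and the new-site stratum shows 0.80 × 1.09 = 0.87 up to 0.80 × 1.39 = 1.11.

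**If SBBC-I capture also changed**
- s = 1.1, c = 0.9: 16.4/13.6 = 1.21 (m = 1) and 18.4/15.6 = 1.18 (m = 3).
- s = 1.1, c = 0.7: 16.4/10.8 = 1.52 and 18.4/12.8 = 1.44.
- s = 0.9, c = 0.9: 13.6/13.6 = 1.00 and 15.6/15.6 = 1.00. The two changes cancel.
- s = 0.9, c = 0.7: 13.6/10.8 = 1.26 and 15.6/12.8 = 1.22.
- s = 1.1 with no new-site under-capture (c = 1): 16.4/15 = 1.09 and 18.4/17 = 1.08.

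**Check against the coded model.** A binomial regression on expected counts used the section 3.2 terms for SBBC-I, intervention and time only, with time linear, an assumed death rate of 1.2%, an assumed SBBC-I share of births of 30% and s = 1. The spurious ratio of ORs (new/SBBC-I) at 18 months was 1.10-1.11 for c = 0.9, 1.22-1.25 for c = 0.8 and 1.37-1.42 for c = 0.7. The model therefore does not remove the artefact. The Stata code has no SBBC-I by intervention term without time, so a group-specific step has to be taken up by that group's time slope.

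**The case against.** The best defence is that the SAP plans no formal inference on this contrast. Item d is a heterogeneity term in a model for overall efficacy, the stratum RRs are a supplement, p-values are exploratory and causal claims are excluded. With different baseline sources, giving the groups their own effects is sensible, and section 7 already discloses the larger driver, retrospective under-reporting. All of this stands, and it limits the weight of the point. It does not answer it: an exploratory label deals with multiplicity, not with a bias whose direction at the new sites the SAP itself gives, and the disclosure is not carried through to the comparison between groups.

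Three stronger readings are tempting, and the document does not support them.

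- A reader might infer that recording moved in opposite directions in the two groups, so that SBBC-I facilities must look better. The SAP never says that the phase I system captured more deaths than later extraction. Directly recorded times of death show finer timing, not fuller capture.
- A reader might infer that later book data hold no direct information on early death. Section 2.1 makes an exception for NICU admissions.
- A reader might apply under-capture to the whole baseline, allow SBBC-I capture of 1.0-1.1, and quote an SBBC-I/new ratio of 0.7/1.1 = 0.64 to 0.9/1.0 = 0.90 as the expected bias. That ignores the 1-3 prospective months and excludes values of s below 1 without evidence.

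It is also fair to object that a baseline limited to March 2024 onward is short and overlaps preparation. Preparation and awareness of being observed may act differently in experienced and new facilities, so restriction may exchange one differential bias for another. That is why such a fit can only sit beside the main result.

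**Conclusion.** The point holds for the supplementary SBBC-I versus new-facility contrast: the difference in RR, and the difference between the groups' CUSUM charts, can arise from recording alone. With retrospective capture of 0.7-0.9 and unchanged SBBC-I capture, the spurious ratio of RRs (new/SBBC-I) is about 1.09-1.39. These are illustrations that rest on assumed capture, constant monthly births and no preparation effect; they are not estimates of the bias. Only the direction at the new sites comes from the SAP. If SBBC-I capture also changed, the ratio would move further up or back toward 1, and the SAP gives no basis for saying which.

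A reader might take this as showing that the phase I facilities' advantage, if one appears, is false, or that the contrast is the trial's main claim. Neither follows: the calculation shows what recording could produce, and the contrast is secondary by the SAP's own design.

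**What to change.** 1. **Section 7, baseline comparison.** Extend the planned comparison of data before and from March 2024 to the 30 SBBC-I facilities, so that any step at their own change of source is visible.
2. **Section 7, sensitivity analysis.** Beside the main result, report the SBBC-I and new-site RRs with the baseline limited to March 2024 up to intervention start in both groups, at least for perinatal death. Note that intervals will be wide, that the period overlaps preparation, and that maternal deaths are likely to be sparse.
3. **Section 7, caveat.** State that the full-baseline difference in RR between SBBC-I and new facilities may reflect differing changes in recording, and is not interpreted on its own as a difference in effect. This should not depend on whether the fit in (2) agrees: no criterion for agreement exists, and an imprecise fit could settle the matter by chance.

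The cost is SAP wording, one added descriptive comparison and one extra fit per outcome analysed, all on data already being collected. The main efficacy analysis is unchanged.

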In the (likely) case of convergence problems, the model will be reduced in the following order:

- 1. Reducing complexity in the random effects.
- 2. Reducing complexity in the fixed effects by removing higher order interactions.
- 3. Reducing complexity in the fixed effects by reducing the degrees of freedom for the splines of time, ultimately assuming linear effect of time.
- 4. After each reduction in fixed effects, try in the random effects again.

Regarding 1: Experience from SBBC phase I was that the clustering on birth level (for multiples) was difficult to account for without convergence issues. If the same problem is encountered here and not resolved by removing random intervention effects at two levels, we will resort to the same solution as used in phase I, i.e., including only one of the babies in births with multiples.

Once a model has been identified that converges successfully and shows no signs of numerical instability, we will proceed to reducing the fixed effects structure by optimizing Akaike's Information Criterion (AIC). Specifically, any parameter whose removal results in a reduction of the AIC by at least 2 will be excluded from the model. If possible, random effects will be reintroduced.

In SBBC-I, FHR at admission was by far the most important individual-level adjustment variable for perinatal deaths, and for maternal deaths, FHR at admission and ASB were most important. Referral-in (yes/no) was also of some importance. FHR at admission and referral-in are only available in the intervention period here and only on facility level (FHR also in a less informative variable than in SBBC-I), and this is also the case with preterm (yes/no). Thus, in addition to ASB (for maternal outcome), we will in the current analyses have to suffice with adjusting for birth weight (categorical including "missing" as a category), mother's age (non-linear effect), and multiples (yes/no), which all were found to have some adjustment effect in SBBC-I. Since we do not expect changes in the population during the study period, these adjustments will be mostly relevant for comparisons between regions, facility levels, and SBBC-I (yes/no), where changes in referral patterns among the participating facilities during the intervention may play a role.

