The main efficacy analysis will be based on the available cases, assuming missing completely at random (MCAR) missingness in covariates (preliminary assessment of amount of missingness <1%) and missing at random (MAR) missingness in the outcome variables. We do expect some missingness in the outcome variables. For assessing sensitivity to different assumptions regarding missing data in the primary outcomes, perinatal death and 7-days maternal death, we provide sensitivity analyses based on missing not at random (MNAR) best/worst-case scenarios:

- As best-case scenarios we assume all missing being non-fatal outcomes.
- As worst-case scenario for perinatal death, we assume the following missing being fatal outcomes: referred-out cases; birth by CS; BW<1500 grams or missing; those requiring resuscitation using ventilation; low Apgar score (i.e., <7) at 5 minutes, or, if missing at 5 minutes, Apgar score <7 at 1 minute. The rest are assumed non-fatal cases.
- For maternal outcome we assume all missing with antepartum stillbirths, eclampsia, labour complications (3-degree tear, retained placenta, postpartum bleeding, blood transfusion), and referred-out cases to be fatal outcomes in the worst-case scenario.

7 Supplementary and supporting analyses

As a supplement to the main results in 3.2, marginal RRs will be presented according to combinations of factors (region, facility level, SBBC-I) and for different time points in the intervention period.

Although the intervention does not include means to reduce ASB, and does not target directly 2-7 days mortality, these outcomes are adjacent to the primary perinatal outcome and may be influenced indirectly, either due to changes in reporting or through possible postponement of the death event. Thus, it is of interest to assess potential changes in these indicators as well. For this, we will provide plots showing trends in rates of ASB and 2-7 days newborn deaths over the study period.

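### The efficacy model in SAP Section 3.2 lets region, facility level and SBBC-I status change the intervention effect only through time, so all strata share one initial step and early stratum-specific RRs are biased if the true steps differ

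*SAP*

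**What the plan says.** Section 3.2 expects the intervention effect to vary by region, facility level, SBBC-I status and possibly their combinations. Time is measured from intervention start and is zero for all baseline births.

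- **Terms without time.** The syntax lists "i.region i.facility_level i.sbbc_phase1 i.intervention": main effects only.
- **Group terms.** These are "i.region#i.intervention#c.s_time", "i.facility_level#i.intervention#c.s_time" and "i.sbbc_phase1#i.intervention#c.s_time", followed by their higher-order combinations. All carry the time variable.
- **Prose.** Region-specific effects are "modeled through an interaction between region (five regions) and the intervention-by-time spline term". Items c) to e) follow the same pattern, and item d) is introduced as "Differing treatment effects between facilities that were part of SBBC phase I and those new in SBBC phase II".
- **Random effects.** Facilities have random intercepts and random intervention effects. These are the first to be simplified if the model does not converge, and are retried later.
- **Reduction.** The spline for time may be cut back, "ultimately assuming linear effect of time". The AIC step that follows only removes fixed-effect parameters.
- **Outputs.** The primary summary is the overall marginal RR at 1.5 years. Section 7 adds that "marginal RRs will be presented according to combinations of factors (region, facility level, SBBC-I) and for different time points" in the intervention period, and Section 5 adds prediction plots from the final models.

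**The concern.** In Stata a single # creates only the named product and adds no lower-order terms. The model therefore has one intervention step, shared by all strata, and strata may differ only in how the effect develops afterwards. The prose says the same, so this is not a slip in the code.

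That sits badly with the heterogeneity the section anticipates. Thirty facilities continue from phase I and 112 are new. An equal immediate effect in both is a strong assumption that the SAP neither states nor defends. If it is false, the model pulls each stratum's early effect towards the pooled step and then bends the stratum's time course to compensate. A stratum with a constant effect would show a trend that is not there, in the very tables and plots meant to show differences between strata and over time. Nothing later in the plan adds the missing terms.

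**Working it through.** The SAP states no figure on this point, so there is none to reproduce.

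**Step 1: the constraint.** For stratum g at time t after start, the fixed-effect log-OR against baseline is

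log-OR(g, t) = β + f(t)·γ(g),

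where β is the single intervention coefficient and γ(g) collects the common and group-specific time coefficients. A restricted cubic spline basis with 4 knots at 1, 7, 13 and 19 months evaluates to (0, 0, 0) at t = 0, and linear time is zero there too. So log-OR(g, 0) = β for every g. This needs no assumption about rates.

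**Step 2: size, two strata.** Inputs:

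- From the SAP: the model structure. Start in April-June 2024 and data to the end of 2025 give about 18-21 intervention months. Baseline from January 2023 to March 2024 gives 15 months.
- Assumed: true constant OR 0.80 (new) and 1.00 (SBBC-I), new sites holding 50-80% of the information, baseline risk 1.5% in both, no random effects.

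A logistic model with the SAP's fixed-effect structure was fitted to expected counts. The table gives the estimated SBBC-I OR (truth 1.00). Each range runs over the information share and over 18 or 20 intervention months.

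| Time model | Start | 3 months | 18 months |
|---|---|---|---|
| Linear | 0.84-0.90 | 0.87-0.92 | 1.00-1.03 |
| 4-knot spline | 0.84-0.90 | 0.93-0.96 | about 0.99-1.01 |

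The start value is close to the information-weighted step: 0.80^0.5 = 0.894 and 0.80^0.8 = 0.837. New facilities are also estimated at 0.84-0.90 at start instead of 0.80. Adding group × intervention returns exactly 0.80 and 1.00 at every time point.

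**Step 3: a larger difference, and the overall RR.** Assumed: log-OR step −0.4 in 112 new facilities (risk 1.5%) and 0 in 30 SBBC-I facilities (risk 1.0%), no later change, equal births per facility, 15 baseline and 20 intervention months. The true RRs are 0.674 and 1.000.

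| SBBC-I RR at month | 0 | 3 | 6 | 12 | 18 |
|---|---|---|---|---|---|
| SAP model, linear | 0.724 | 0.765 | 0.809 | 0.903 | 1.008 |
| SAP model, 4-knot spline | 0.725 | 0.876 | 1.004 | 0.964 | 0.974 |
| With group × intervention | 1.000 | 1.000 | 1.000 | 1.000 | 1.000 |

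The overall RR at 18 months is weighted by expected baseline deaths, 112 × 0.015 = 1.68 and 30 × 0.010 = 0.30:

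- Truth: (1.68 × 0.674 + 0.30 × 1.000) / 1.98 = 0.723.
- SAP model, linear: (1.68 × 0.669 + 0.30 × 1.008) / 1.98 = 0.720.
- SAP model, spline: (1.68 × 0.677 + 0.30 × 0.974) / 1.98 = 0.722.

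**Step 4: facility random effects.** The Step 3 steps and risks were simulated with 150 births per facility per month, facility random intercepts (SD 0.4) and random steps (SD 0.15), in 6 replicates. The SAP structure gave SBBC-I ORs at start of 0.731 (linear) and 0.721 (spline). With the added term the OR was 1.023.

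**Step 5: control.** When the true steps are equal (log-OR −0.2 in both strata), the SAP model reproduces the truth at all time points.

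**The case against.** **Random effects.** The full model gives each facility its own random step and slope, so only the mean step is common. That is correct, and the SAP plans to retry random effects after simplifying. But they are centred on the common step, are first in line for reduction, and did not remove the early bias in Step 4.

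**Spline basis.** The SAP sets time, not the spline function, to zero and names no basis. A basis carrying a constant could let strata differ at start. This stands as a condition on the finding. Linear time, the stated end of the fallback, does meet the condition.

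**Primary result.** It is the overall RR at 1.5 years, and it barely moves. The affected RRs are supplementary, and their p-values are exploratory under Section 4. This stands and limits the weight of the point.

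**Other analyses.** The CUSUM and VLAD displays use baseline-only models, with separate CUSUM plots by stratum, and Section 3.4 analyses SBBC-I and new facilities separately. None carries the constraint. They give other views of the time course but do not correct the Section 7 RRs.

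**A stronger reading.** A reader might infer that strata where nothing changed would show benefit at start and harm later. Least squares on the log-OR for the Step 2 scenario does give an SBBC-I OR of 1.06-1.09 at month 18, but it treats the baseline as known without error. In the SAP's model the baseline is estimated jointly and absorbs part of the misfit, which leaves 0.99-1.03. Other settings fall below 1: 0.94-0.98 with a 3-knot spline, and 0.92 in the random-effects simulation (0.96-0.97 there with the added term). The SAP does not support a claim of late harm.

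**Conclusion.** The point holds as a specification error that should be corrected. The prose and the code both force one mean initial step on all strata whenever the time function is zero at start, against the heterogeneity that the SAP itself anticipates. If true initial steps differ, stratum-specific RRs and prediction plots for the early months are biased towards the pooled step and show a false trend. For a true contrast of 0.80 against 1.00, the SBBC-I OR at start is about 10-16% too low, and the error largely fades by month 18 with linear time or a 4-knot spline.

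The constraint itself follows from the algebra. The sizes depend on the assumed steps, rates, information shares and knots, and vanish if the steps are equal. It would be wrong to infer that the primary estimate is compromised: in the example it changed by less than 0.5%.

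**What to change.** Add `i.region#i.intervention`, `i.facility_level#i.intervention` and `i.sbbc_phase1#i.intervention` to items b) to d) and to the syntax. For every higher-order group-by-time interaction that is kept, add the matching group-by-intervention term. State that all reductions, for convergence or by AIC, respect hierarchy: a group-by-time term goes before its group-by-intervention step. Name the spline basis and choose one with f(0) = 0, so that the step is identifiable.

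The cost is a few lines of text and syntax. The two-way steps take 4 + 2 + 1 = 7 parameters. Keeping all higher-order steps would add up to 8 + 4 + 2 + 8 = 22 more if every combination of factors exists, in a model where the SAP already expects convergence trouble. This can be offset by dropping the highest-order slope interaction first: with a 4-knot spline (3 time columns) that alone frees up to 8 × 3 = 24 parameters.
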